7.7 Missing Data

Missing data may occur in the proposed study in several ways. First, it may be due to item non-response. In these cases, we will prorate total scores for a measure by taking an average score on the measure and multiplying it by the total number of items in the scale. Attrition can result in missing data due to missed assessments or dropout from the study. Prior to performing any outcome analyses, we will evaluate the amount, reasons, and patterns of missing data. Missing data unrelated to the outcome of interest will be considered missing completely at random (MCAR), and complete case analysis will still generate unbiased estimates.(89) For the missing values at the baseline or partial baseline collected data, we will use a multiple imputation approach.(89) We will conduct sensitivity analyses to compare estimates of treatment effects with and without multiple imputation to assess the effect of missing data on statistical inference.

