Study Outcomes. The pilot study will be used to assess the preliminary efficacy of MyPEEPS Mobile for YTM. Our primary outcome will be the number of condomless receptive anal and/or vaginal sex acts with either a cisgender male or transgender woman. To estimate the effect size for a larger clinical trial, we will focus on the primary outcome of: Condomless receptive anal or vaginal sex acts. The measures listed in Table 6 have been used in our MyPEEPS trial and piloted with 49 YTM as part of our formative work for this application. We will collect all measures at baseline, 3 and 6 months, other than demographic variables which will only be collected at baseline. We also ask participants to report on their own knowledge of their most recent partners' use of PrEP or ART medications. Given the unreliability of perceptions of partner-related risk in particular(71), we will use these data for a secondary sensitivity analysis (see below). This study is not powered for efficacy or tests of moderation or mediation; nonetheless, the purpose of the inclusion of these factors is to measure the impact of the intervention on

them as intermediate targets given their potential role in behavior change.

Table 6. Outcome Measures

Demographics

Sociodemographic (e.g., age, race/ethnicity level of education, housing status)

Newest Vital Sign(72)

Short Test of Functional Health Literacy (S-TOFHLA)(73)

Transgender Congruence Scale(74)

Measures of Hormone Use

Primary Outcome Measures

Condomless receptive anal and/or vaginal sex (adapted from AIDS-Risk Behavior Assessment)(68-70)

Intermediate Outcome Measures

Self-efficacy for safer sex and situational temptation for unsafe sex(75)

Condom Errors(76)

Health Protective Communication Scale(77)

HIV-Knowledge Questionnaire – HIV-KQ-18(78)

Alcohol and Substance Use(79)

Sexual Behavior Index(80)

Secondary Outcomes

nPEP and PrEP Use

Self-reported HIV and STI Testing

Partner(s) PrEP Use, PrEP Adherence or Viral Suppression (if partner is HIV+)

Program Evaluation

Knowledge of and beliefs about the content of the MyPEEPS Mobile intervention

MyPEEPS intervention acceptability and tolerability(81)

Paradata

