Data Analysis. All multivariate analyses will be preceded by standard descriptive bivariate analyses to describe key variables and relationships among key variables. These analyses will include means, frequency tables, histograms, and examination of distributions. All statistical tests will be two-sided tests with the level of significance at 0.05(60).

Outcomes: This study will examine whether the intervention will reduce the number of condomless receptive anal or vaginal penile sex with either a cisgender male or transgender woman; the primary outcome is a count measure (Table 6 - Outcome Measures). We assume that all count outcome variables follow Poisson or negative binomial (NB) distribution, $y \sim \text{Poi}(\lambda)$ or $y \sim \text{NB}(\lambda, \kappa)$ and all percentage outcomes follow binomial distribution, $y \sim \text{bin}(n, p)$. Let the expected value of outcome, $E(y) = \varphi$, so $\varphi = \lambda$ for count outcomes and $\varphi = p$ for binary outcomes. We propose the following generalized linear mixed model (GLMM) to analyze all outcomes. The level of analysis

will be assessed at each data point. For person i and data assess wave W (i.e. baseline, 3, and 6 months):

$$+ \mu_i,$$

where $h(\cdot)$ is the link function for the GLMM. We will use log-links (Poisson or NB regression) for count

Table 7. Codes for design variables

Months	Intervention			Delayed Intervention		
	Arm	W	INT	Arm	W	INT
Baseline	0	0	0	1	0	0
3 mos	0	1	1	1	1	0
6 mos	0	2	1	1	2	1

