8.4.2 General Risks

There may be risks or discomforts in participating in this study. Participants may feel uncomfortable with the HIV prevention information that is provided and completing some questions in the survey. Participants may skip any HIV information or questions that may make them feel uncomfortable or stop the research procedure. People around may observe participants using the MyPEEPS Mobile application. If participants are concerned about people seeing them use of MyPEEPS Mobile, it is important that they access the application in private location.

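### Section 7.7 prorates partly answered measures with no minimum number of answered items, no exclusion for act counts, and an unresolved overlap with the baseline imputation rule.

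*Combined protocol and SAP*

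**What the plan says.** Section 7.7 (Missing Data) opens its list of causes with "First, it may be due to item non-response", and the response is to "prorate total scores for a measure by taking an average score on the measure and multiplying it by the total number of items". No minimum number or fraction of answered items is given. No measures are named as covered or excluded.

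The same section adds a second rule: "For the missing values at the baseline or partial baseline collected data, we will use a multiple imputation approach". It does not say how this fits with proration when a baseline measure is only partly answered. The planned sensitivity analyses will "compare estimates of treatment effects with and without multiple imputation". None varies the use of proration.

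Section 7.6 states: "Our primary outcome will be the number of condomless receptive anal and/or vaginal sex acts" with a cisgender male or transgender woman partner, and adds that "the primary outcome is a count measure". Table 6 says the measure is adapted from an existing risk-behaviour assessment. Neither place gives its number of items or how a total is formed. Table 6 also lists the HIV-KQ-18 knowledge questionnaire as an intermediate outcome, without a scoring rule for blanks.

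Skipping is expressly allowed. Section 8.4.2 says: "Participants may skip any HIV information or questions that may make them feel uncomfortable". Sections 8.2.1 and 8.4.1 also let participants decline questions.

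**The concern.** Multiplying the mean of the answered items by the number of items is reasonable when the items are roughly interchangeable and most have been answered. Section 7.7 requires neither condition. A total can therefore rest on a single response and still enter the analysis as if fully observed.

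Act counts are the sensitive case. Anal and vaginal acts, or acts with different partner types, need not occur at similar rates, so one is a poor stand-in for another. Section 7.7 gives no other item-level rule at follow-up, and Sections 4.5 and 7.2 place the primary endpoint at 3 months. An analyst facing a partly answered count at that visit would find only the proration sentence. At baseline the analyst would find two rules. Section 4.5 defines the primary outcome as a change, so one participant's change could combine an imputed baseline with a prorated follow-up.

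What is at stake is the pilot's main quantitative product. Section 7.6 uses its effect sizes and within-outcome correlations to size a later trial. Both depend on means and variances that proration can alter.

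**Working it through.** The plan gives no figure on this point to reproduce. The check applies the rule as written.

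**Formula (Section 7.7).** Prorated total = (sum of answered items ÷ number answered) × number of items.

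**Knowledge test.** 18 items, taken from the instrument's name.
- 14 correct of 17 answered: 14 ÷ 17 × 18 = 14.8
- 8 correct of 9 answered: 8 ÷ 9 × 18 = 16.0
- 1 correct of 1 answered: 1 ÷ 1 × 18 = 18.0

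The first result is unremarkable. The last is a full score from one response. What the right score would be depends on how blanks are treated, which the documents do not say.

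**Act count, assuming separate items.** The item structures and counts here are assumptions.
- Two items, 12 reported, other skipped: 12 ÷ 1 × 2 = 24
- Two items, 0 reported, other skipped: 0 ÷ 1 × 2 = 0, even if the skipped item held 5
- Two items, 2 reported, skipped item truly 10: 2 ÷ 1 × 2 = 4, against a true 12
- Four items, 10 reported in one, three skipped: 10 ÷ 1 × 4 = 40

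**Effect on an arm mean.** If one participant is scored 24 when the true total is 12, the arm mean rises by 12 ÷ 40 = 0.30 acts with all 40 per arm, or 12 ÷ 32 = 0.375 acts at the 80% retention target (40 × 0.80 = 32).

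**Average effect.** Let the two items have means m1 and m2, and let a fraction q skip item 2 at random. The prorated mean divided by the true mean is 1 + q(m1 − m2) ÷ (m1 + m2). For means 9 and 3 with q = 0.20, this is 1 + 0.20 × 6 ÷ 12 = 1.10. A simulation (independent negative binomial items, dispersion 0.5, total mean 12, 400,000 draws) agrees and adds the variance:

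| Item means, vaginal:anal | Fraction skipping one item | Mean ratio, anal skipped | Variance ratio, anal skipped | Mean ratio, vaginal skipped |
|---|---|---|---|---|
| 6:6 | 5% | 1.000 | 1.05 | 1.000 |
| 6:6 | 10% | 0.999 | 1.10 | 1.000 |
| 6:6 | 20% | 1.000 | 1.20 | 1.001 |
| 9:3 | 5% | 1.025 | 1.13 | 0.976 |
| 9:3 | 10% | 1.051 | 1.28 | 0.950 |
| 9:3 | 20% | 1.099 | 1.54 | 0.901 |
| 11:1 | 5% | 1.042 | 1.16 | 0.958 |
| 11:1 | 10% | 1.083 | 1.33 | 0.916 |
| 11:1 | 20% | 1.166 | 1.64 | 0.833 |

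With equal item means and random skipping there is extra variance but no bias in the mean. With unequal means the bias goes up or down according to which item is skipped.

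**Effect on a ratio of means.** If skipping and item mix are the same on both sides of a comparison, the factor cancels. If they differ, it does not. At 9:3, with 20% skipping the anal item on one side and 5% on the other, the ratio is off by a factor of 1.10 ÷ 1.025 = 1.07.

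**The case against.** The strongest reply is that Section 7.7 speaks of total scores and of items in a scale, which is the language of multi-item questionnaires, whereas Section 7.6 calls the primary outcome a count. On that reading act counts were never meant to be prorated, and if the count is one question the rule cannot touch it. This stands as far as it goes. A reader might infer that the plan will fabricate primary-outcome acts; the documents do not support that, because they never give the item structure or say that counts are prorated. There are hints of separate items. Section 7.6 says the measures were used in the earlier MyPEEPS trial, and Section 1.4 reports that trial's insertive and receptive acts separately. The partner sensitivity analysis in Section 7.6 refers to anal sex alone. These are hints, not proof.

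A reader might also infer that prorated scores are always too high, or that the errors can never average out. The calculations show otherwise for counts, and for the knowledge test the direction depends on an unstated rule for blanks. Nor do the documents describe the scoring of the literacy tests or behaviour inventories in Table 6, so the point is not extended to them.

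The plan has other safeguards. Section 7.7 examines the amount, reasons and patterns of missingness before outcome analysis, Sections 7.3.2 and 7.3.3 check distributions and outliers, and Table 5 treats missing data as a feasibility measure. These may reveal heavy skipping, but they set no minimum and do not test proration. Finally, this is a pilot not powered for efficacy, and no sample-size or power figure changes. That limits the severity without removing the gap.

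**Conclusion.** The concern holds in limited form. It is certain from the text that the proration rule has no minimum answered, no list of covered measures and no exclusion for counts, that it overlaps with baseline multiple imputation without reconciliation, and that no sensitivity analysis tests it. A total resting on one answered item is permitted as written.

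Distortion of the primary outcome is conditional on that count being summed from separate items and on proration being applied to it. Confidence in that consequence is moderate. Under the assumed two-item structures with 5% to 20% skipping, the mean would be 0.83 to 1.17 times its true value, and the variance 5% to 64% higher when the anal item is the one skipped. The item means, dispersion and skip rates are all assumptions, because the documents give none. That discomfort would lead participants to skip sexual items in particular is plausible but not shown.

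**What to change.** Rewrite the item non-response paragraph of Section 7.7 to:

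- limit proration to named multi-item summed scales with a pre-set minimum fraction answered (80%, for example; the exact cut-off is a judgement), and state how blanks on the knowledge test are scored;
- state that the primary act count and other behaviour counts are never prorated: if a component is missing, the total is missing at that wave and is handled by the likelihood-based GLMM or by multiple imputation extended to follow-up, since imputation is now named only for baseline;
- state whether proration or multiple imputation governs partial baseline data;
- add a sensitivity analysis without proration;
- report how often proration was used, by measure, wave and arm.

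If the primary count is a single question, one sentence saying so settles that part.

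The cost is a paragraph of text and one extra analysis. A few totals become missing, so nominal completeness falls slightly. Setting a partial count to missing is not free of bias if skipping depends on the unreported value, but the missingness is then visible and can be examined.

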7.1 DATA MANGEMENT, SECURITY & ANALYSIS

7.2 Power Considerations and Sample Size Calculation (Aim2)

Sample Size and Power Calculation. The study plan is to enroll 80 participants with 1:1 random assignment to the intervention arm and the control arm (i.e., 40 in each arm). Compared to a large- scale randomized trial, we do not expect that this pilot trial will have power to detect many of the effects that would be of scientific or policy significance. This is consistent with the aims of this pilot grant mechanism, where budgetary limitations necessitate small sample sizes. Group means on continuous variables typically begin to stabilize by 20-30 participants. Thus, a sample size of 40 participants per group should provide relatively stable group means for the intervention and control conditions, even with some sample attrition.

Study Design. Participants in the intervention group will be able to access the MyPEEPS intervention from baseline until the end of month 3, and the control arm (delayed intervention) will have access to the MyPEEPS App from months 4-6.

Overview of Data Collection Time Points. We will conduct simultaneous assessments for both study arms at baseline, 3 months, and 6 months. We will also collect an immediate post-intervention assessment for the delayed intervention arm. The delayed intervention design is essentially a cross-over design in which data are collected in parallel from both study arms through the primary endpoint - 3 months post-randomization. The arms are then crossed over, which has multiple benefits, including: 1) for ethical reasons per our experience with transgender populations, the delayed intervention group receives the potential benefit of the intervention at the point of cross-over; 2) at the 6-month follow-up, it provides for a test of the durability of the intervention effect in the intervention group (i.e., 3 months post-intervention, pre-post); 3) it provides an additional secondary test of the intervention effect in the delayed intervention arm (pre-post); and 4) it provides additional time points (and power) in the intervention group, to test moderators of the trajectory of sexual risk over time.

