7.3.3 Data Monitoring

For the study, weekly reports for the sites will be created by the data manager to review relevant app engagement data, barriers with recruitment/enrollment and retention, urine sample collection, compliance with the protocol, and accuracy and completeness of the records. The investigative team will hold reoccurring conference calls, and these reports will be briefly reviewed by the team at these meetings. These regular reviews will ensure close communication between the research assistants, quickly identify missing data points, and ensure consistent management of any issues with the protocol between sites.

Data quality will be examined before statistical analyses are conducted, including examination of missing data, assessment of distributional assumptions, and identification of outliers. In addition to data quality, the comparability between intervention and control groups will be carefully examined, including baseline balance and differential attritions at all waves of follow-up. While differences are not expected from the randomized design, it is prudent to plan for this

contingency so that sufficient follow-up data and appropriate statistical methods can be used for intent-to-treat analyses.

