7.5.1 Procedures to Ensure Compliance with Monitoring Plan and Reporting Requirements

Biweekly reports for the sites will be created by the study statistician to review relevant app engagement data, barriers with recruitment/enrollment and retention, laboratory and medical records, compliance with the protocol, and accuracy and completeness of the records. The

investigative team will schedule biweekly conference calls, and these reports will be briefly reviewed by the team. These regular reviews will ensure close communication between the research assistants, quickly identify missing data points, and ensure consistent management of any issues with the protocol between sites.

7.6 Data Analysis Plan for Aim 2

Assessment of feasibility and acceptability of the intervention (Table 5). We have specified the following measures of feasibility and acceptability: Retention Rates, Compliance Rates, Dose, Eligibility Criteria, Recruitment and Enrollment, Missing Data, Study Measures(68-70).

Table 5. Measures of Feasibility and Acceptability of MyPEEPS Mobile for YTM

Constructs	Measures	Threshold (if applicable)
Retention Rates	-How many enrollees remain in the study? -Are they about the same in both arms?	At least 80% will remain in the study.
Compliance Rates	What is the completion rate of app sessions by participants?	At least 80% will have completed at least 75% of the intervention content.
Dose	Is the dose of the intervention e.g., number of sessions adequate (assessment of paradata).	Does the dose need to be adjusted?
Eligibility Criteria	Are eligibility criteria acceptable, or do they need modification because they are too stringent?	Eligibility rates (number of individuals eligible among those approached)
Recruitment and Enrollment	What is the pace of recruitment? Barriers to recruitment and enrollment	
 Rates of refusal (number of refusals vs. enrolled among those approached) Rates of no shows
Missing Data Measures	What is the extent and patterns of missing data? Length of time and burden to the respondents	The survey questions (Number and Type) may need to be adjusted

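### Section 7.7 rests missing follow-up on a loose, unverifiable MCAR label and an undefined complete-case analysis, and does not link either to the wave-level GLMM

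*Combined protocol and SAP*

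**What the plan says.** Section 7.7 separates three situations. Item non-response is prorated within a scale. Missing baseline values are multiply imputed. For missed assessments and dropout, the team will look at the amount, reasons and patterns of missingness, and the section then states: "Missing data unrelated to the outcome of interest will be considered missing completely at random (MCAR), and complete case analysis will still generate unbiased estimates". A sensitivity analysis compares treatment effects with and without multiple imputation.

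The outcome model is in section 7.6: "We propose the following generalized linear mixed model (GLMM) to analyze all outcomes". It has a person-level random intercept and is written for each person and wave, with the design codes in Table 7. The waves are fixed in section 7.2: "We will conduct simultaneous assessments for both study arms at baseline, 3 months, and 6 months". The same section says that "data are collected in parallel from both study arms through the primary endpoint - 3 months post-randomization".

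Sections 7.3.2 and 7.3.3 promise a check of arm comparability, "including baseline balance and differential attritions at all waves of follow-up", and refer to intent-to-treat analyses with appropriate but unnamed methods. The retention target in Table 5 is "At least 80% will remain in the study".

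**The concern.** Three things do not fit together.

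- **The label.** Missingness can be unrelated to the outcome yet related to arm or to another characteristic, and it is then not MCAR. Observed data can contradict MCAR but cannot establish it, because the unseen month-3 and month-6 counts are part of the condition.
- **The coverage.** Imputation is described for baseline values only, so the with/without-imputation comparison does not probe missing follow-up counts. Complete-case analysis is left as the only approach named for attrition, and nothing is said for the case where missingness does relate to the outcome.
- **The link to the model.** Section 7.7 never mentions the GLMM and never says whether a complete case is a person with all three waves or a single wave with its data present.

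The protocol itself gives reasons to doubt MCAR. Section 6.5 lists repeated non-compliance with the intervention and a reported HIV diagnosis among the grounds for leaving the study. Controls have no app access until the month-3 visit (section 4.5), so before the primary time point the non-compliance ground can act only in the intervention arm. The HIV ground is plausibly related to sexual risk.

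At stake are the size and direction of the pilot's effect estimate, which section 7.6 intends to use for sizing a later trial.

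**Working it through.** Section 7.7 gives no figure, so there is nothing of the plan's own to reproduce.

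**Inputs from the documents**
- Size (section 7.2): "The study plan is to enroll 80 participants with 1:1 random assignment to the intervention arm and the control arm (i.e., 40 in each arm").
- Retention: at least 80% (Table 5).
- Waves: baseline, 3 and 6 months, with month 3 primary (section 7.2).
- Model: Poisson or negative binomial GLMM, log link, random intercept, Arm/W/INT as in Table 7 (section 7.6).
- Illustrative effect: rate ratio 0.55 (section 7.6, future-trial power example).

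**Step 1: how many month-3 counts depend on the definition**

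Retained: 0.80 × 80 = 64 (32 per arm). Lost: 80 − 64 = 16. Take these 16 as the people lacking at least one follow-up wave.

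- All attrition at month 6: 80 month-3 counts exist. A three-wave completers analysis keeps 64 and drops 16 (16/80 = 20%).
- All attrition before month 3: no month-3 count exists for those 16, so none is dropped.
- Complete case taken wave by wave: none is dropped in either case.

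The range is therefore 0 to 16 of 80.

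**Step 2: effect on the estimate**

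Data were simulated from log E(y) = β0 + β1·Arm + β2·W + β3·INT + u, with u normal and y negative binomial, and true exp(β3) = 0.55. The model was fitted by maximum likelihood to (a) all observed waves and (b) three-wave completers only.

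Assumptions not in the documents: baseline mean of 5 acts, random-intercept SD 1.0, negative binomial size 2, and dropout at month 6 only. Dropout is 20% over both arms together, so its amount as well as its mechanism can differ by arm. Where it depends on a count, the log-odds slope is 1.5 per unit of log(1 + count). The plan does not say whether W is categorical or numeric, so both were run (300 and 200 replicates).

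| Month-6 dropout | W categorical: all waves / completers | W linear: all waves / completers |
|---|---|---|
| MCAR | 0.55 / 0.55 | 0.54 / 0.54 |
| Driven by month-3 count, alike in both arms | 0.55 / 0.57 | 0.57 / 0.59 |
| Driven by month-3 count, control arm only | 0.54 / 0.69 | 0.54 / 0.68 |
| Driven by month-3 count, intervention arm only | 0.55 / 0.43 | 0.55 / 0.45 |
| Driven by month-3 count, opposite directions by arm | 0.56 / 0.37 | 0.54 / 0.42 |
| Driven by the unseen month-6 count, alike in both arms | 0.56 / 0.55 | 0.54 / 0.53 |

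The Monte Carlo standard error of the all-waves estimates is about 0.02 on the log scale.

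**Step 3: reading the table**
- Under true MCAR both analyses are unbiased. Completers only costs precision: the SD of the log rate ratio rises from 0.277 to 0.311 (0.311/0.277 = 1.12) with W categorical.
- With outcome-related dropout alike in both arms, the error is small: 0.57/0.55 = 1.04.
- With outcome-related dropout that differs by arm, the error is material and can go either way: 0.69/0.55 = 1.25, 0.43/0.55 = 0.78, 0.37/0.55 = 0.67.
- The all-waves GLMM stays at 0.54 to 0.57 throughout.

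**The case against.** The sentence in section 7.7 is conditional, and under true MCAR it is correct. The GLMM in section 7.6 works at the level of the person-wave, so dropping incomplete records there would remove only the missing wave. The secondary-outcomes paragraph adds that analyses use the final data set with 80 at baseline, and sections 7.3.2 and 7.3.3 speak of intent-to-treat. Missing at random cannot be verified either, so the replacement also carries an untestable assumption. The study is an 80-person pilot, stated not to be powered for efficacy, and missing data are themselves one of its feasibility measures.

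Much of this stands. Two stronger readings should be set aside. A reader might infer that the plan discards recorded month-3 counts. It does not say so; that follows only if a complete case means a three-wave completer, which the documents leave open. A reader might also infer that a test of MCAR decides which analysis is run. Section 7.7 promises a review of amount, reasons and patterns, but contains no test, threshold or alternative analysis.

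The objection does not remove the gap. Nothing in section 7.7 points to the wave-level model, and its only named approach to attrition rests on a stricter assumption than that model needs when fitted by likelihood.

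**Conclusion.** The point holds as a correctable weakness in section 7.7. The MCAR definition is too loose and cannot be verified, complete-case analysis is the only approach named for attrition, and its meaning within the GLMM is unresolved.

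The size depends on the definition and on the dropout. Read wave by wave, no observed count is lost. Read as three-wave completers, the simulated rate ratio can fall anywhere from 0.37 to 0.69 against a true 0.55 when outcome-related dropout differs by arm. It would be wrong to conclude that bias is certain: it is absent under MCAR and small when dropout acts alike in both arms.

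The simulated values rest on the assumed rates, dispersion and dropout slopes, and on the fitted model matching the one that generated the data. The ranking of the two analyses under missing at random does not depend on those particular values. The simulation does not show that the all-waves analysis is safe under arm-differential dropout driven by unseen counts, which was not examined.

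**What to change.** Replace the MCAR and complete-case sentence in section 7.7 with:

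> *All randomised participants with any outcome data are analysed by maximum likelihood in the GLMM using all available waves, under missing at random; complete-case results are not primary.*

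If complete-case results are still reported, define the term. A sensitivity analysis for follow-up counts that are not missing at random would be a sensible addition, because the existing with/without-imputation comparison does not reach them.

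The cost is a wording change in the analysis plan. It needs no new data, no new model and no change to the assessment schedule.
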